3. LIST OF ABBREVIATIONS

CRF	Case Report Form
CRO	Contract Research Organization
CV	Curriculum Vitae
DB	Database
AE	Adverse Event
ICH	International Conference on Harmonization of Technical Requirements for Registration of Pharmaceuticals for Human Use
IEC/IRB	Independent Ethics Committee/Institutional Review Board
JPS	JuniOrtho™ Plating System™
MDDs	Medical Device Deficiencies
PMCF	Post-Market Clinical Follow-up
QOL	Quality of Life
ROM	Range of Motion
SAE	Serious Adverse Event
SOA	State-of-art
WBI	Weight Baring Index

4. SYNOPSIS

TITLE	A single center, post-market clinical follow up (PMCF) observational study evaluating the clinical performance and the safety profile of the JuniOrtho™ Plating System™ (JPS) for the treatment of congenital deformities and fractures in lower limbs of pediatric and adult patients.
ACRONYM	OCI_JPS
MEDICAL DEVICE (MD)	
JuniOrtho™ Plating System™ (JPS)
 
JPS is a complete plating system designed to address the specific demands of advanced deformity and trauma reconstruction of the lower extremities in pediatric population. Moreover, where bones size is appropriate, JPS can also be applied on adult patients. The system was designed for the treatment of proximal femur, distal femur, proximal and distal tibia fractures, where plating is one of the options.

RATIONALE	
Orthofix Srl put the JPS on the European market (2019) by the mean of a pre-market clinical evaluation made under the Medical Device Directive (MDD) requirements that were based on the analysis of the scientific literature of equivalent devices.
 
This study has been planned as part of the Orthofix Srl post-market active surveillance plan for the collection of data on both the clinical performance and the safety profile of the JPS in a representative population of patients and users.
 
The rationale of the proposed study is to update and support the pre-market clinical evaluation of the JPS with real-word-evidence clinical data, in order to confirm the benefit/risk ratio of this medical device and to keep the CE mark under Medical Device Regulation (MDR) requirements.

STUDY DESIGN	PMCF Study: Post-market, observational (retrospective and prospective), single-center, not controlled.
PROCEDURES	
One selected site that is experienced in the treatment of pediatric and adult patients with bone deformities and fractures, where the usage of JPS is already part of the normal clinical practice, will participate in this study. Investigator will provide data for a maximum of 40 JPS implant cases satisfying inclusion and exclusion criteria (predicted drop out rate is 10%) that will contribute for at least 30 cases treated by JPS (note that some patients may contribute for more than one JPS case, according to how many JPS implants were received).
 
For retrospective study cohort, who has previously had JPS implanted and follow-up assessment and JPS removal is done, the investigators shall purely collect clinical data from the medical record of the subjects, concerning the screening criteria, the surgery (MD application) and 4 following events: hospital discharge, first post-application control, bone consolidation assessment and device removal. Data from patients' observation are collected according to the site standard-of-care.
 
Patients, who are prospectively enrolled in the study and have undergone JPS implantation, will have follow-up assessments, as described on Table 10.2, or until patient withdrawal.

[figure not shown]
	
The patient data will be systematically collected by the investigator in eCRF. As per CIP, the subjects will not undergo additional visit nor non-invasive, invasive or burdensome procedures additional to those performed under the normal clinical practice.
					
OBJECTIVES	
The objectives of this study are to assess:
 
 - the safety profile (primary objective) - the clinical performance (secondary objective) 
of the JPS within the scope of its intended purpose, when used according to the manufacturer IFU on a representative population of subjects and users.
					
SAFETY ENDPOINTS	
The safety profile of JPS will be assessed by the following safety endpoints:
 
 - Percentage (%) of subjects with at least one serious/not serious adverse event certainly related or possibly related to JPS (ADEs) (primary safety endpoint) at device removal follow-up (up to 18 months according to site's standard practice); - Percentage (%) of MD Deficiencies (MDDs) at device removal follow-up (up to 18 months according to site's standard practice). 					
EFFICACY ENDPOINTS	
The clinical performance of JPS will be assessed by the following efficacy endpoints:
 
 - Percentage (%) of subjects that reached a satisfactory bone consolidation according to investigator's opinion (primary efficacy endpoint); - Percentage (%) of subjects that maintained bone correction alignment according to investigator's opinion until device removal. 					
PLANNED STUDY PERIOD	First Patient in	4Q 2022	Last Patient in	2Q 2023	DB closure	2Q 2024 (anticipated)
STUDY DURATION FOR THE SUBJECT	Provided the study is observational. The estimated time of patient observation period is 18 months.					
SITE(S) / COUNTRY(IES)	1 Investigational Site in Germany					
PATIENTS / GROUPS	
Clinical data to be collected only on patients with a regular indication for JPS as per IFU (no off-label use will be included): the system is intended in pediatric (excluding newborns) and small stature adult (that according investigator judgement the patient's anatomy is deemed suitable for the use of JPS plate). Pediatric patients include infants (greater than 1 month to 1 years of age), children (greater than 1 to 12 years of age), adolescents (greater than 12 to 18 years of age) and appropriate adults (where according to investigator assessment, the JPS plates fit the treated bone anatomy).
					
INCLUSION CRITERIA	
A patient will be eligible for inclusion in the study if:
 
 • had a regular indication for surgical intervention with JPS according to the manufacturer's IFU; • underwent a surgery for bone deformity correction or trauma reconstruction of the lower extremities performed by JPS; • the clinical data registered in her/him patient chart are sufficient to assess the safety and efficacy endpoint of the study (for retrospective patients); 					

	
 • patient (or his/her legally acceptable representative) is capable of understanding the content and is willing to sign the Informed Consent Form (ICF) • patient is willing and able to participate in the data collection and comply with the protocol requirements;
EXCLUSION CRITERIA	
A patient will be excluded from participation in the study if he/she:
 
 • had/has a medical condition that is a contraindication according to the manufacturer's instruction for use leaflet; • had/has a concomitant not permitted device which cannot be safely removed; • patient for whom there are other concurrent medical or other conditions that in the opinion of the participating investigator may prevent participation or otherwise render patient ineligible for the study.
COMPARATIVE DEVICE	Not applicable (the study is not controlled)
PERMITTED CONCOMITANT DEVICE	K-wires and any other concomitant devices, i.e. bone screws, that were applied to fix any bone fragments but that were not considered critical for the maintenance of treated bone alignment, are permitted during the treatment. It is understood that any necessary medical devices applied on any other bones other than the one treated by JPS are permitted as well.
QUALITY OF LIFE (QOL)	
A QOL questionnaire is not performed in the normal clinical practice of the site participating this study. Provided clinical data will be retrospectively collected, it will not be possible to report a QOL questionnaire as a study result. Anyway, when available, the range of motion (ROM) of the treated limb and the weight bearing index will be collected and assessed as representative variables for the evaluation of the QOL of the enrolled Subjects.

STATISTICAL METHODOLOGY	
Hypothesis to test: the observed primary safety endpoint for JPS ranges within the state-of-art (SOA) safety profile of equivalent plating systems.
 
Primary safety endpoint: the proportion of subjects (% \pm the upper and lower limit of the 95 % confidence interval) with at least one serious/not serious adverse event surely or possibly related to JPS.
 
State of art: The proportion of subjects with serious/not serious adverse event related or possibly related to the device reported in the scientific literature for the treatment of congenital deformities and fractures in lower limb of pediatric and appropriate adult patients by the means of equivalent plating systems is between 5.1 % and 15.0 % depending on many factors, mainly the diversity of the primary diagnosis.
 
Assumption: for the sole purpose of the sample size calculation, it was required to assume an expected proportion of subjects for the primary safety endpoint of JPS. The sample size, therefore, was calculated estimating the required number of subjects so that the upper limit of the 95% confidence interval for the expected proportion is ranged within the SOA (i.e. 95% CI upper limit \leq 15 %).

	
Sample size calculation: assuming the expected proportion of patients with at least one serious/not serious adverse event surely or possibly related to JPS will be 3 %, and assuming the worst case of each patient contributing for only one JPS implant case: 30 subjects was calculated to be the sample size of this study so that the upper limit of the 95 % confidence interval for the primary endpoint, based on the exact binomial method, is under 15 %. Considering that one patient can contribute for one JPS implant, and considering a 10% drop out rate, the site can enroll a maximum of 40 JPS implant cases.

INTERIM ANALYSIS	
An interim analysis, not planned at the start of the study, will be performed after at least 20 subjects will be enrolled and completed the "Bone Consolidation" event. The aim of this interim analysis is to verify the consistency of testing hypothesis and to confirm the historical data on the medical device safety and performance. Interim results will be used to prepare the Clinical Evaluation Report (CER).
 
To preserve the integrity of the study results interpretation, a correction for multiplicity due to two planned analyses (interim+final) will be implemented using the approach proposed by O'Brian-Fleming for sequential design (Shein –Chung Chow et Al Sample size calculations in Clinical Research 2003, Christopher Jennison et Al Group Sequential Methods with applications to clinical Trials,2000)
 
For this purpose, sample size will be recalculated using this approach (all details are reported in the cited bibliography):
 
 - The initial sample size will be correct by factor 1.008 for a two-sided test at 5% level and 80% power. The final sample size is $30*1.008=30.2$ - The probability level will be correct by factor 1.977, at interim the P value will be 0.0052 while at the final analysis P value will be 0.048. The corresponding confidence limits will at interim 99.5% and at final analysis 95.2% 
In conclusion, applying the O'Brian-Fleming approach to control the type I error no great impact on sample size is observed and integrity of clinical study is preserved from any interpretation bias.

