5.2 Rationale of the Clinical Investigation and justification of vulnerable group

Orthofix Srl put the JPS on the European market (2019) by the mean of a pre-market clinical evaluation made under the Medical Device Directive (MDD) requirements that was based on the analysis of the scientific literature of equivalent devices.

This study has been planned as part of the Orthofix Srl post-market active surveillance plan for the collection of data on both the clinical performance and the safety profile of the JPS in a representative population of patients and users.

The rationale of the proposed study is to update and support the pre-market clinical evaluation of the JPS with real-word-evidence clinical data, in order to confirm the benefit/risk ratio of this medical device and to keep the CE mark under Medical Device Regulation (MDR) requirements.

The uniqueness of the pediatric population manifests itself in specific indications for lower extremity reconstruction, mostly due to congenital deformities or conditions; different approach in compliance with postoperative care or need for adaptability to rapid growth and development. The JuniOrtho™ Plating System™ (JPS) is a well established, marketed device, commercially available and used as standard device in orthopedic surgeries.

The post-marketing, retrospective/prospective study with CE-marked device JuniOrtho™ Plating System™ (JPS) is designed for gathering real-world medical data from treatment of congenital deformities and fractures in lower limb of pediatric and in small stature adult patients.

All data will be collected from standard medical documentation of patients who have already been treated with JPS. Additionally, all procedures that patients underwent are justified by standard of care.

Constant identification of serious or unexpected serious risk related to the use of the device, especially in real-world experience may bring additional data, that can contribute to the safety of future patients.

In conclusion, patients will not directly benefit from the participation in this study but no additional risk related to the study participation is to be recognized.

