7.2 Subjects and Sites Numbers

This study will be conducted only on patients with a regular indication for JPS as per IFU (no off-label use will be included): the system is intended in pediatric (excluding newborns) and small stature adult patients. Pediatric patients include infants (greater than 1 month to 1 years of age), children (greater than 1 to 12 years of age) and adolescents (greater than 12 to 18 years of age) and appropriate adults (where according to investigator assessment, the JPS plates fit the treated bone anatomy).

This study includes only one site (monocentric) that is located in Wetter (Germany). The site was chosen for this study due to the number of subject devices already implanted, and the wideness of the indications covered by the surgeries. The site was also positively evaluated by sponsor for the appropriate qualification and competency of the investigator and of the staff, and availability of facilities and equipment.

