8. SELECTION AND WITHDRAWAL OF SUBJECTS

8.1 Subject Inclusion Criteria

A patient will be eligible for inclusion in the study if:

- had/has a regular indication for surgical intervention with JPS according to the manufacturer's IFU;
- underwent a surgery for bone deformity correction or trauma reconstruction of the lower extremities performed by JPS;
- the clinical data registered in her/him patient chart are sufficient to assess the safety and efficacy endpoint of the study (for retrospective patients);
- patient (or his/her legally acceptable representative) is capable of understanding the content and is willing to sign the Informed Consent Form (ICF);
- patient is willing and able to participate in the data collection and comply with the protocol requirements

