10.2 Description Event by Event

10.2.1 V0: Screening and Baseline

Prospective patients who meet the eligibility criteria will be enrolled in the study. Patients who agree to enter the study must sign the approved Informed Consent Form. Consented patients will have performed assessments as outlined in this protocol.

During the screening the investigator will evaluate the eligibility of the patients, checking all inclusion and exclusion criteria. Only those patients who meet all inclusion and exclusion criteria will be enrolled in the study. For each JPS implant a unique case number will be assigned (ID), and reported in the eCRF. Considering that each patient can contribute for more than one JPS implant: one patient can have more than one ID. In the eCRF the IDs are linked to the first ID assigned to the same patient by the clinical site. The patients not enrolled for non compliance will be considered as screening failures and will not be entered in the eCRF. Only for the enrolled patient, the Investigator will collect the demographic data and the medical history of the patient including information concerning the limb to be treated with JPS (baseline) such as the radiographic images and clinical examination.

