14.6 Data Handling and retention

The sponsor and the investigator assume the responsibility to assure that the clinical data will be collected according to the CIP requirements (no additional data will be collected), local laws and obligations and the World Medical Association Declaration of Helsinki. The clinical data obtained as a result of this study is considered confidential between the site and the sponsor: disclosures to third part are prohibited or, if necessary for example to perform statistical analysis with contracted vendors, will be protected by non-disclosure agreements.

Before the Site Initiation Visit, the sponsor will provide a validated eCRF system and will train the Investigators about the data entry procedures, data clearing and queries resolution. Only the data recorded in the eCRF will be considered for the statistical analysis. The clinical data entered in the eCRF must come from the source data, that is all information in original (or certified copies) patients' clinical records, records of clinical findings, investigator's observations/assessment.

The investigator assumes the responsibility to assure that the last data will be entered within 2 week from the plate removal of the last patient.

The investigator will have to keep all study related documentation for the longest possible duration, but at least for 15 years after the completion or premature termination of the study. No data should be destroyed without agreement of the sponsor. The Sponsor will maintain all documentation pertaining to the study for the lifetime of the product.

Sponsor and investigators shall take measures to prevent accidental or premature destruction of these documents and they may rely on a third part for documents retention by a non-disclosure agreement to protect data confidentiality.

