16 DESCRIPTIVE STATISTICAL ANALYSIS

16.1 PATIENT DISPOSITION

A summary of patients included in the study, as well as those who are non-evaluable and the reasons for this will be shown.

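### Cases are capped at 40 but need not be consecutive, and patients left out appear in neither the eCRF nor the planned report, so selection related to the primary endpoint would not be visible there

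*Protocol*

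**What the plan says.** **How cases enter.** Under Procedures, the Protocol Synopsis states: "Investigator will provide data for a maximum of 40 JPS implant cases satisfying inclusion and exclusion criteria". Protocol 7.2 explains the choice of site: "The site was chosen for this study due to the number of subject devices already implanted", and adds the breadth of indications as a second reason. Neither document contains a consecutive or all-comer rule, a surgery-date window, a retrospective/prospective split, or a rule for choosing if more cases qualify than are needed.

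**What is known at that moment.** The Synopsis describes one cohort as "For retrospective study cohort, who has previously had JPS implanted and follow-up assessment and JPS removal is done"; Protocol 10.1 and 13.2 define it the same way.

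**Where judgement enters.** Protocol 8.1 requires, for retrospective patients, a chart sufficient to assess the safety and efficacy endpoints. Protocol 8.2 lets the investigator exclude a patient for other conditions that, in the investigator's view, make the patient ineligible. Consent (13.2) is a further filter.

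**What is recorded.** Protocol 10.2.1: "The patients not enrolled for non compliance will be considered as screening failures and will not be entered in the eCRF". Protocol 14.6: "Only the data recorded in the eCRF will be considered for the statistical analysis". SAP 16.1 promises: "A summary of patients included in the study, as well as those who are non-evaluable and the reasons for this will be shown". SAP 13 takes evaluable and non-evaluable status from the screening items in the CRF.

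**The concern.** The study has no control group. Its primary result is one percentage, set against literature rates of 5.1% to 15.0% and offered as the safety profile in a representative population. How cases are ascertained is therefore a main safeguard of validity.

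For retrospective cases, the plan lets the person who supplies the case see the related-adverse-event status first. It gives no order in which to take cases, and it provides no account in the analysed data of who was left out. If event cases were less likely to be put forward, the primary percentage would be too low, and a reader of the report would have no means of seeing or bounding it.

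**Working it through.** **Inputs from the documents.** Expected rate 3%, 30 subjects, exact binomial upper limit under 15% (Protocol 12.2); cap of 40 implant cases (Synopsis); two-sided Clopper-Pearson intervals at 95.2% for the final analysis (SAP 14). **Not in the documents:** the number of JPS implants at the site and the retrospective share.

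**1. The plan's own figure.** The exact upper limit for x events in n subjects is U = Beta⁻¹(1 − a; x + 1, n − x), where a is the upper-tail probability. The expected count is 0.03 × 30 = 0.9, so x = 1.
- One-sided 95% (a = 0.05): U(1, 30) = 14.86%, and 30 is the smallest n at or below 15%. The stated 30 reproduces on this basis.
- Two-sided 95% (a = 0.025): U(1, 30) = 17.2%, and 35 subjects would be needed.

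The one-sided or two-sided question is a separate matter. The steps below use the SAP's own interval, a = 0.048/2 = 0.024.

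**2. Effect of one substituted patient (95.2% limits, one implant per patient).**

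| Events | n = 30 | n = 40 |
|---|---|---|
| 0 | 11.7% | 8.9% |
| 1 | 17.4% | 13.3% |
| 2 | 22.2% | 17.0% |

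The smallest n with the limit at or below 15% is 23 for no events, 36 for one and 46 for two. So for n from 30 to 35, replacing one event patient by an event-free patient crosses 15% at the step from one event to none. For n from 36 to 40 it crosses at the step from two events to one. The step from one to none at n = 40 (13.3% to 8.9%) crosses nothing.

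**3. Illustration under assumptions.** Take n = 40, where at most one event keeps the limit at or below 15%. The pool sizes and the relative chance of inclusion are assumed.

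| How the 40 are obtained | True rate 10% | True rate 15% |
|---|---|---|
| Consecutive: P(X ≤ 1), X ~ Bin(40, p) | 8.0% | 1.2% |
| Event cases half as likely to be supplied | 37.1% | 15.4% |
| Suitable 40 exist among 42 eligible | 38.4% | 10.7% |
| Suitable 40 exist among 45 eligible | 84.1% | 47.8% |
| Suitable 40 exist among 50 eligible | 99.7% | 93.7% |

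Row 2 uses the effective rate 0.5p/(0.5p + 1 − p): at p = 0.15 this is 0.075/0.925 = 8.1%. The last three rows use P(X ≤ M − 39) with X ~ Bin(M, p), because 39 event-free cases are enough. They are an extreme, in which the 40 are chosen freely with outcomes in view. With a pool of exactly 40 there is no choice, and the figure returns to row 1.

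**4. Would it be seen?** Protocol 10.2.1 keeps screening failures out of the eCRF; Protocol 14.6 restricts the analysis to the eCRF; SAP 13 derives evaluability from CRF items. The SAP 16.1 table can therefore show only patients who were entered. It cannot show those screened out, nor eligible patients never approached.

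**The case against.** A reader might infer that selection would leave no trace and that the sponsor could not detect it. The documents do not support that. Protocol 13.3 mentions a patient screening log at the site, 14.2 plans full source verification of the eligibility criteria, 14.3 gives monitors access to all source data, and 14.4 allows audit. What stands is narrower. The log appears only in a confidentiality clause, and nothing requires it to list every JPS implant, to be reconciled with implant records or to be reported. Nor does anything extend source verification to eligible patients never approached.

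A reader might also infer that most cases are retrospective. Protocol 7.2 and the statement in Protocol 5.2 that "All data will be collected from standard medical documentation of patients who have already been treated with JPS" make a sizeable share plausible, but no split is given.

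The 15% limit is also not a stated success rule. Protocol 12.1 and 12.2 use it to set the sample size, Protocol 12.4 assesses the hypothesis descriptively, and the SAP names no criterion. The crossing is therefore a yardstick for sensitivity, not the reversal of a defined decision.

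The direction of any bias is not shown either. Chart sufficiency covers both safety and efficacy, and nothing says that event cases fail it more often.

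Finally, last patient in was planned for 2Q 2023 and the SAP was signed in April 2024, so a new inclusion rule may come too late. That limits the remedy, not the point.

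**Conclusion.** The point holds as a gap in how cases are selected and accounted for. Followed exactly, the plan permits choice with the outcome in view in the retrospective cohort, and such choice would not appear in the eCRF or the planned report. Within the planned 30 to 40 subjects, one substituted patient can move the 95.2% upper limit across 15%: 17.4% to 11.7% at n = 30, or 17.0% to 13.3% at n = 40.

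This rests on one implant per patient, on at least one retrospective case, and on more cases being eligible than are enrolled; the documents do not give the last two numbers. It does not show that cases were selected on outcome or that the reported percentage will be too low.

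**What to change.** - **Protocol 7.2, 8.1 and 10.2.1:** require inclusion in order of surgery date from a stated start date, whatever the outcome, up to the cap.
- **Site log:** require it to list every JPS implant in that window with the reason for any non-inclusion (chart not sufficient, no consent, investigator opinion, other criterion), and reconcile it with the site's implant records.
- **SAP 16.1:** report implants listed, approached, consented and excluded, with reasons, by cohort. Use aggregate counts from the log. Patient-level eCRF entries for people who did not consent would sit badly with the consent requirement in Protocol 13.2 and the bar on additional data in 14.6.
- **If enrolment is complete:** carry out the reconciliation and aggregate reporting, and state in the report whether inclusion was consecutive.

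The cost is wording in both documents and a little more site time. Consecutive order also removes the investigator's freedom to choose cases, which is its purpose. No extra patients, visits or procedures are needed.
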